## SYNOPSIS: Intravital Microscopy (IVM) in Human Solid Tumors

PI: [name] [name]

Co-PI: [name]

[name]

[name]

[name]

[name]

[name]

Statistician: [name], MS

Study Center: Mayo Clinic Florida

Concept and Rationale: Intravital microscopy (IVM) allows real-time, direct visualization of microscopic blood vessels and calculation of blood flow. Our group has used IVM in mouse models to characterize aberrant blood vessel structure surrounding tumor implants and the associated impaired lymphocyte trafficking along these tortuous vessels.[1] These preclinical studies have been translated to human intravital microscopy (HIVM) in a pilot study that analyzed the tumor-associated microvasculature at primary melanomas.[2] The feasibility of HIVM was 90% at the primary tumor. As an extension of this completed trial, [name] had implemented an on-going clinical trial (NCT02857374, Intravital Microscopy in Identifying Tumor Vessels in Patients with Stage IB-IIIC Melanoma Undergoing Sentinel Lymph Node Biopsy) that investigates the role of IVM in analyzing the vessels associated with sentinel lymph nodes. In addition, with members of the multidisciplinary team listed, above, we have also implemented a trial in HIVM at Mayo Clinic Florida that investigates HIVM in patients with peritoneal carcinomatosis, NCT03517852 Intravital Microscopy (IVM) in Patients with Peritoneal Carcinomatosis (PC). This proposed trial at Mayo Clinic Florida will further determine the usefulness of IVM in human subjects, now applying it to patients with intra-abdominal or retroperitoneal tumors as well as study the effects of fluid shifts on the tumor blood flow in real time.

In this clinical trial proposal, the following aims will be addressed:

Aim 1: Determine the feasibility of HIVM in characterizing the tumor-associated vessels in patients with deep space solid tumors and correlate these findings with patient outcomes. We hypothesize that HIVM will be feasible in deep space solid tumors and function as a predictive biomarker for response to systemic therapy.

Aim 2: Determine the effects of dynamic control on tumor vessel blood flow during surgical resection. We will investigate whether we can reproduce enhanced tumor blood flow, established in our previous animal models, in human subjects using our dynamic control protocol (consisting of a fluid bolus and vasopressors, routinely given during the course of surgery).

Objectives:

*Primary objective(s):* To determine the feasibility of performing HIVM in patients with deep space solid tumors during standard course of surgical resection. A successful intravital microscopic observation will include the ability to complete each of the following:

1. Identify and measure vessels associated with tumor
2. Determine vessel density per 10x field
3. Visualize vital dyes within the vessels (fluorescein)
4. Calculate the blood flow velocity of the vessels and tissue penetration of fluorescein as a marker of vessel permeability.
5. Obtain these vessel parameters after administration of an IV fluid bolus and/or vasopressor administration (phenylephrine or vasopressin) during the normal course of the surgical resection.

*Secondary objective(s):*

1. Compare the microscopic observation of the tumor-associated vessels with normal tissue (e.g. peritoneal surface) in each individual subject.
2. Correlate the microscopic observations of the tumor-associated vessels with pathologic grade of tumor.
3. To correlate the microscopic observation of the microvasculature with tumor-specific and overall survival.

Study Design: This is a non-randomized, single center, study of HIVM observation in subjects with deep space solid tumors undergoing surgical resection.

All subjects will meet the inclusion and exclusion criteria prior to participation in this study. Standard evaluation by the Preoperative Anesthesia clinic at Mayo Clinic Florida may include additional testing such as EKG, chest x-ray, and/or pulmonary function tests.

The study will be performed in two parts. Part 1 will enroll 10 patients with an expected feasibility rate of 70%. Whereas the feasibility rate in primary melanoma was 90%, the expected feasibility rate for deep space tumors may be lower as the site is in an anatomically deeper location. If Part 1 is not met (i.e. in three or more patients), the primary objective would not be considered technically feasible, and then the study will be stopped. If Part 1 is fulfilled, then the study will continue with an additional 40 patients enrolled (total of 50 patients). Accrual is expected to take 2.5 years.

*Inclusion criteria:*

1. Age  $\geq$  18 years of age.
2. ECOG Performance Status of  $\leq 2$ .
3. Measurable tumor by direct visualization requiring surgical resection in the OR.

4. Tumor types of origin include gastric, pancreatic, hepatobiliary, colorectal, and sarcoma. Tumors may be primary or metastatic to solid or hollow intra-abdominal organs.
5. Subject must understand the investigational nature of this study and sign an Independent Ethics Committee/Institutional Review Board approved written informed consent.
6. Subject must have a skin prick test pre-operatively (at the time of the preoperative visit and after signed informed consent for entry into this clinical trial is given) to determine any sensitivity to fluorescein.

*Exclusion criteria:*

1. Uncontrolled intercurrent illness including, but not limited to, ongoing or active infection, symptomatic congestive heart failure, unstable angina pectoris, cardiac arrhythmia, or psychiatric illness/social situations.
2. Renal dysfunction as defined as a GFR < 45.
3. Liver dysfunction as defined by Child-Pugh score > 5, or LFT's 1.5x above normal range.
4. Any known allergy or prior reaction to fluorescein or a positive skin prick test to fluorescein.
5. Pregnant or nursing female subjects, determined preoperatively with a urine pregnancy test.
6. Unwilling or unable to follow protocol requirements.
7. Any condition which in the Investigators' opinion deems the patient unsuitable (e.g., abnormal EKG, including T wave inversion, elevated T waves, prolonged QRS interval, or conduction blocks) or that requires further work-up (including cardiac echo or stress test).
8. Any condition that excludes surgery as the standard of care (e.g. high disease burden where alternative treatments like systemic chemotherapy would be preferred).

Primary and Secondary Endpoints/Criteria for Evaluation:

*Primary endpoint:* A patient will be deemed a success if each of the following parameters were measured:

1. Identify tumor associated vessels and measure vessel diameters
2. Determine vessel density per 10x field
3. Visualize vital dyes within the tumor-associated vessels (fluorescein)
4. Calculate the blood flow velocity of the tumor-associated vessels and tissue penetration of fluorescein as a marker of vessel permeability.

Measurements will be obtained before and after any tumor vessel manipulation with either bolus fluids or vasopressors.

*Secondary endpoints:*

1. Post-operative comparison of the microvasculature of tumor with normal tissue (e.g. peritoneum) in each individual subject using vessel diameters, vessel density, detection of intravital dye and flow rates.
2. Post-operative correlation of the microvasculature with pathologic features of the tumor (i.e. tumor grade) at the time of the final pathology report (5-7 days after surgery).

3. Post-operative correlation of the microscopic observation of the tumor microvasculature tumor-specific and overall survival.

**Subject Name:** \_\_\_\_\_

**Medical Record No.:** \_\_\_\_\_

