## **9 STATISTICAL METHODOLOGY**

Initially ten patients will be treated to determine the feasibility of HIVM for deep space tumors. This first part of the study is a pilot study of feasibility. If seven or more patients are deemed a success by meeting all of the criteria below, then HIVM will be deemed feasible in the study of deep space tumors. Criteria include the ability to complete each of the following:

1. Identify and measure vessels associated with tumor
2. Determine vessel density per 10x field
3. Visualize vital dyes within the vessels (fluorescein)
4. Calculate the blood flow velocity of the vessels and tissue penetration of fluorescein as a marker of vessel permeability.

If the true success rate is 60%, the probability of deeming HIVM feasible is 63%; if the true success rate is 70%, then the probability of deeming HIVM feasible is 88%; and if the true success rate is 90%, then the probability of deeming HIVM feasible increases to 99%.

If HIVM is deemed feasible, then an additional 40 patients will be accrued to this study in order to address the following:

1. Post-operative comparison of the microvasculature of tumor with normal tissue (peritoneum) in each individual subject using vessel diameters, vessel density, detection of intravital dye and flow rates.
2. Post-operative correlation of the microvasculature with pathologic features of the tumor (i.e. tumor grade) at the time of the final pathology report (5-7 days after surgery).
3. Post-operative correlation of the microscopic observation of the tumor microvasculature tumor-specific and overall survival.

An abnormal HIVM observation is defined by any of the following criteria:

1. Aberrant vessel structure compared to normal tissue, which includes tortuosity of the vessel wall or a closed loop formation.
2. Aberrant vessel branching patterns compared to normal tissue, which includes erratic and disorganized branching points.
3. Blood vessel density that is less than or greater than one standard deviation of the blood vessel density observed in normal tissue.
4. Inability to detect flow or fluorescein within a vessel.
5. Average blood flow rate through observed vessel that is less than one standard deviation of the average blood flow rate through a normal vessel.

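### Seven successes in the ten Part 1 patients, the single likeliest result at the expected 70% rate, stops the study under the synopsis and continues it under Section 9

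*Combined protocol and SAP*

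**What the plan says.** The Study Design part of the synopsis sets the size and expectation of Part 1, "Part 1 will enroll 10 patients with an expected feasibility rate of 70" per cent, and then a stop rule: "If Part 1 is not met (i.e. in three or more patients), the primary objective would not be considered technically feasible". The synopsis makes termination the consequence of that finding: "and then the study will be stopped".

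Section 9 (Statistical Methodology) sets a go rule for the same ten patients: "If seven or more patients are deemed a success by meeting all of the criteria below, then HIVM will be deemed feasible". The consequence is enrolment: "If HIVM is deemed feasible, then an additional 40 patients will be accrued to this study".

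Section 9 also prints the chance of passing at three true success rates: "If the true success rate is 60%, the probability of deeming HIVM feasible is 63" per cent; "if the true success rate is 70%, then the probability of deeming HIVM feasible is 88" per cent; and "if the true success rate is 90%, then the probability of deeming HIVM feasible increases to 99" per cent.

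Section 4.2 replaces patients lost to equipment malfunction or to unrelated intraoperative events and does not count them as failures. No section says whether the synopsis or Section 9 prevails if they differ.

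**The concern.** With ten evaluable patients, three failures and seven successes are the same result. The synopsis calls it not feasible and ends the trial. Section 9 calls it feasible and opens enrolment of 40 more patients.

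This is the only prespecified statistical go/no-go rule in the protocol. It fixes both the primary feasibility conclusion and whether 80% of the planned sample (40 of 50) is enrolled. The study is open-label (Section 4.1), so the count is known as it accrues. If it ends at 7 of 10, the team would have to choose between two written rules with the result in hand. Continuing would depart from the synopsis and stopping would depart from Section 9. Nothing suggests that such a choice is intended, but the text leaves it open.

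**Working it through.** **Inputs**

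- Part 1 size: n = 10 (synopsis, Section 9). Replacement under Section 4.2 keeps the denominator at 10.
- Expected success rate: 70% (synopsis).
- Synopsis: stop at 3 or more failures, so go requires X ≥ 8 successes.
- Section 9: go at X ≥ 7 successes.
- Printed chance of passing: 63%, 88% and 99% at true rates of 60%, 70% and 90% (Section 9).

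**Formula.** With X ~ Binomial(10, p), P(X = x) = C(10, x) pˣ (1 − p)¹⁰⁻ˣ, and P(go) is the sum of these terms from the threshold to 10.

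**Step 1: the plan's own figures**

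| Rule (n = 10) | p = 0.6 | p = 0.7 | p = 0.9 |
|---|---|---|---|
| Printed in Section 9 | 63% | 88% | 99% |
| X ≥ 6 | 63.3% | 85.0% | 99.8% |
| X ≥ 7 (Section 9) | 38.2% | 65.0% | 98.7% |
| X ≥ 8 (synopsis) | 16.7% | 38.3% | 93.0% |

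Under Section 9's own rule only the 99% is reproduced. Under the synopsis rule none is. The printed 63% equals X ≥ 6 at a true rate of 60% (63.3%), and the printed 88% equals X ≥ 7 at a true rate of 80% (87.9%). Sample sizes of 9, 11 and 12 were also tried, and no single rule gives all three figures. The printed probabilities therefore cannot be used to infer the intended threshold.

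**Step 2: where the rules differ.** X ≥ 7 and X ≥ 8 disagree only at X = 7. At p = 0.7:

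- P(X = 7) = 120 × 0.7⁷ × 0.3³ = 120 × 0.08235 × 0.027 = 0.2668
- P(X = 8) = 45 × 0.7⁸ × 0.3² = 0.2335
- P(X = 6) = 210 × 0.7⁶ × 0.3⁴ = 0.2001

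Seven is the most probable single count.

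**Step 3: effect on the decision**

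| True rate | P(X = 7) | P(go), X ≥ 7 | P(go), X ≥ 8 |
|---|---|---|---|
| 60% | 21.5% | 38.2% | 16.7% |
| 70% | 26.7% | 65.0% | 38.3% |
| 80% | 20.1% | 87.9% | 67.8% |
| 90% | 5.7% | 98.7% | 93.0% |

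At 70% the synopsis rule stops the study with probability 1 − 0.383 = 61.7%. The Section 9 rule does so with probability 1 − 0.650 = 35.0%.

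**The case against.** The strongest reply is that this is a slip in a summary. The synopsis sentence is elliptical: it never says failures, so the eight-success threshold is inferred. Section 9 is the dedicated statistical section, states its rule directly and attaches probabilities to it. Its threshold of 7 of 10 also matches the 70% that the synopsis expects. A careful reader would probably follow Section 9. At a true rate of 90%, the rate reported for primary melanoma, the overlap is missed about 94% of the time; even at 70% it is missed about 73% of the time.

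Part of this stands. The synopsis threshold is a reading, and likeliest means the most probable single count, not a probability above one half. But no other workable reading of the synopsis sentence is available. It is a complete rule with its own consequence, so it is more than a loose summary. The protocol gives no order of precedence, and Section 9's probabilities do not support its own rule at two of the three rates.

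A further point complicates the comparison. The synopsis primary objective lists a fifth success criterion, measurements after a fluid bolus or vasopressor, which Section 9 and Section 3.1 omit. If it counts, the same ten patients could yield different success counts under the two texts. That adds to the need for reconciliation.

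**Conclusion.** The contradiction is real and should be corrected. The two sections set thresholds one success apart, and 7 of 10 falls under both. At the expected 70% rate that outcome has probability 26.7%, and the choice of rule moves the chance of proceeding from 65.0% to 38.3%. Over true rates from 60% to 90% the probability of landing on the overlap runs from 5.7% to 26.7% at the rates tabulated.

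This rests on ten evaluable patients, independent outcomes with a common success rate, one definition of success applied under both rules, and the natural reading of the synopsis as counting patients in whom the objective is not met. The contradiction itself does not depend on any assumed success rate.

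**What to change.** State one threshold, in the same terms (successes out of ten evaluable patients), in the synopsis and in Section 9. The sponsor must choose which.

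- **If seven or more successes is kept**, the synopsis trigger changes from three or more to four or more patients. This fits the expected 70% better, since the eight-success rule would stop the study 61.7% of the time at that rate. The Section 9 probabilities become 38.2%, 65.0% and 98.7% at 60%, 70% and 90%.
- **If eight or more is intended**, Section 9 changes instead, and the probabilities become 16.7%, 38.3% and 93.0%.

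In the same amendment, use one list of success criteria throughout and say whether the post-bolus or post-vasopressor measurements count.

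The cost is a few lines of text, IRB approval under Section 12.1, and no change to sample size, procedures or data collection. It should be settled before the Part 1 count is known.

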**Title: Intravital Microscopy (IVM) in Human Solid Tumors**

INCLUSION CRITERIA				
Y	N	N/A	All answers must be "YES or "N/A" for subject enrollment.	Date
			1. Age $\geq$ 18 years of age.	
			2. Have an ECOG Performance Status of $\leq$ 2. Refer to Appendix B.	
			3. Have measurable disease by direct visualization (visible lesion typically $> 0.5$ cm in maximal diameter).	
			4. Deep space tumor that meets indications for resection.	
			5. Subject must understand the investigational nature of this study and sign an Independent Ethics Committee/Institutional Review Board approved written informed consent form prior to receiving any study related procedure.	
			6. A negative skin-prick test to fluorescein.	

EXCLUSION CRITERIA				
Y	N	N/A	All answers must be "NO" or "N/A" for subject enrollment	Date
			1. Uncontrolled intercurrent illness including, but not limited to, ongoing or active infection, symptomatic congestive heart failure, unstable angina pectoris, cardiac arrhythmia, or psychiatric illness/social situations.	
			2. Renal dysfunction as defined as a GFR $< 45$ .	
			3. Liver dysfunction as defined by Child-Pugh score $> 5$ , or LFT's 1.5x above normal range.	
			4. Any known allergy or prior reaction to fluorescein or a positive skin prick test to fluorescein.	
			5. Pregnant or nursing female subjects, determined preoperatively with a urine pregnancy test.	
			6. Unwilling or unable to follow protocol requirements.	
			7. Any condition which in the Investigators' opinion deems the patient unsuitable (e.g., abnormal EKG).	
			8. Any condition that excludes surgical resection as the standard of care for the patient.	

## 1 BACKGROUND

Intravital microscopy (IVM) is the microscopic observation of living tissue in real time. IVM has been successfully applied to the investigation of the tumor microvasculature of human primary melanoma.[3] It has been shown that tumor vessels lack the sequential hierarchy of normal vessels such that arterioles, capillaries, and venules typically cannot be discriminated within tumor tissues.[4, 5] This disorganization of aberrant tumor vessels was demonstrated in a previous feasibility clinical trial.[2] These tumor-associated vessels were characterized by irregular diameters, aberrant branching patterns, abnormal blood flow rates, and anastomotic structures. More specifically, the human tumor-associated vessel diameters observed in real time *in vivo* were larger than those predicted either by *in vivo* mouse models or by human immunohistochemistry (IHC) on tumor specimens analyzed *ex vivo*.[3] These characteristics could have profound influence on the delivery of agents (i.e., chemotherapy or cellular immunotherapy) to the tumor microenvironment.[6]

In order to obtain this data, human intravital microscopy (HIVM) was used first in melanoma primary tumors. Intravital microscopy (IVM) has also been used to directly examine the hemodynamic properties of tumor microvessels in preclinical mouse models.[1, 7-9] These studies were primarily based on the analysis of blood vessels and leukocytes labeled *in situ* with fluorescent tracking dyes (e.g., fluorescein). Recent mouse studies in B16 murine melanoma have used IVM to demonstrate that the abnormal, tortuous vascular structure in tumors represents a bottleneck to adoptive cell transfer immunotherapy because of poor trafficking of cytotoxic effector T cells at this site.[1] Others have used different forms of IVM to observe lymphatics or metastatic disease in real time in mouse models.[10, 11] There has also been reported real time imaging of human tumor and lymphatics using different techniques such as multiphoton imaging, high resolution ultrasound, or optical coherence tomography.[12, 13] With support from the 2018 Mayo Clinic Florida Focused Research Teams (FRT) Award Program, our group is actively investigating HIVM for patients with peritoneal carcinomatosis through NCT03517852: Intravital Microscopy (IVM) in Patients with Peritoneal Carcinomatosis (PC). However, there have been no studies of IVM in the setting of deep space solid tumors.

The detection of blood flow parameters (including vessel diameter, flow rates, vessel density, and fluorescent markers of tissue diffusion) in deep space solid tumors of patients may have utility in characterizing the clinical response of these patients to systemic therapies. In addition, because many of these patients require intraoperative fluid boluses and vasopressor support, both of which are known to alter blood flow dynamics, the use of real time HIVM may reveal the ability to control tumor-associated vessels. It is anticipated that this approach has the potential to generate a more complete picture of the tumor-associated locoregional vasculature. The investigation of tumor-associated vessels in real time may lead to a better understanding of factors influencing systemic drug efficacy. Reflective of the study's two specific aims, our approach has the strong potential to expand upon novel tumor imaging techniques and not only form a directly observed basis of the tumor vasculature as a barrier to systemic drug efficacy in humans, but also establish a rationale means to overcome this barrier through standard intraoperative practice.

## **1.1 DIAGNOSTIC INTERVENTION - FLUORESCEIN**

Drug Information - Fluorescein is delivered intravenously during the course of this observation. Fluorescein is an FDA approved drug for visual angiography. The package insert is shown in Appendix A. A single dose consists of a 5 mL vial of 10 or 25% fluorescein and costs \$3.90.

Fluorescein has a very rare incidence of anaphylactic reaction (1 in 222,000), but a skin-prick test may allow these patients to be recognized.[14] Therefore, any reported sensitivity to fluorescein will be considered an exclusion criteria as well as a positive skin-prick test performed during the routine preoperative visit (at least 1 week prior to surgery). The skin-prick test will be performed at the time of the preoperative visit if the patient decides to enter the clinical trial and signs the informed consent. Patients that are not eligible for the study or do not give consent to participate in the study will not undergo a skin-prick test.

The skin-prick test will be performed by the Principal Investigator using a sterile Duotip® lancet (Lincoln Medical, USA) in 2 separate areas of skin on the forearm. The skin-pricks will include 4 microliters of 10% fluorescein administered in areas of skin prepped with an alcohol pad. After 30 minutes, the appearance of a wheal greater than 3 mm in diameter is considered a positive test result. If a positive test is noted, the patient will no longer be eligible for this study. For comfort and relief of any skin irritation/pruritis, the patient will be offered an anti-histamine (fexofenadine [Allegra®] 30 mg po x 1) following the skin-prick test if necessary.

The package insert for fluorescein (which is a commonly used agent in the OR and readily available to the anesthesiologist in their PYXIS system and does not require delivery from pharmacy or an order to pharmacy) is attached in the Appendix section.

The fluorescein will be provided by the study. It will be ordered and sent to surgery for the patient at the time of the planned microscopic observation.

